4. SUBJECT POPULATION

Adult subjects age 18 and older with extranodal NK/T-cell lymphoma, nasal type, are eligible for the study.

Screening for eligible subjects will be performed within 21 days before Cycle 1, Day 1, before administration of the study drug.

The inclusion and exclusion criteria for enrolling subjects in this study are described in the following 2 subsections. If there is a question about the inclusion or exclusion criteria below, the

investigator must consult with the appropriate sponsor representative and resolve any issues before enrolling a subject in the study. Waivers are not allowed.

For a discussion of the statistical considerations of subject selection, refer to Section 10.2, Sample Size Determination.

4.1. Inclusion Criteria

Each potential subject must satisfy all of the following criteria to be enrolled in the study:

1. At least 18 years of age
2. Documented as histologically confirmed extranodal NK/T-cell lymphoma, nasal type according to the World Health Organization (WHO) classification,^{10,13,20} and the pathology report will be verified by the Sponsor.
3. Criterion modified per Amendment 1:
 - 3.1 Failed (relapsed or refractory after achieving complete or partial remission) at least 1 line of chemotherapy, and who, according to treating physician or investigator, is not candidate to receive other treatment modalities.
4. Criterion modified per Amendment 1:
 - 4.1 At least 1 measurable site of disease (see Section 8.2.1), which should be positive ¹⁸F-fluorodeoxyglucose (FDG) uptake in nodal or extranodal sites on positron emission tomography (PET) scan.
5. ECOG performance status score of 0, 1 or 2. (refer Attachment 1) and life expectancy ≥ 3 months.
6. Subject must have pretreatment clinical laboratory values meeting the following criteria during the Screening Phase:
 - a. hemoglobin ≥ 7.5 g/dL (≥ 4.65 mmol/L) without transfusion support within 7 days;
 - b. absolute neutrophil count (ANC) $\geq 0.75 \times 10^9/L$ (ie, $\geq 750/\mu L$) without growth factor support within 7 days;
 - c. platelet count $\geq 50 \times 10^9/L$ without transfusion support within 7 days;
 - d. aspartate aminotransferase (AST) ≤ 2.5 x upper limit of normal (ULN);
 - e. alanine aminotransferase (ALT) ≤ 2.5 x ULN;
 - f. total bilirubin ≤ 1.5 x ULN, except in subjects with congenital bilirubinemia, such as Gilbert syndrome (in which case direct bilirubin ≤ 1.5 x ULN required);
 - g. calculated creatinine clearance of ≥ 30 mL/min (refer Attachment 5: Calculation of Creatinine Clearance using Cockcroft-Gault formula);
7. Criterion modified per Amendment 1:
 - 7.1 Women of childbearing potential must commit to either abstain continuously from heterosexual sexual intercourse or to use 2 methods of reliable birth control simultaneously. This includes one highly effective form of contraception (tubal

ligation, intrauterine device, hormonal [birth control pills, injections, hormonal patches, vaginal rings or implants] or partner's vasectomy) and one additional effective contraceptive method (male latex or synthetic condom, diaphragm, or cervical cap). Contraception must begin 4 weeks prior to dosing. Reliable contraception is indicated even where there has been a history of infertility, unless due to hysterectomy.

8. Criterion modified per Amendment 1:
 - 8.1 A man who is sexually active with a woman of childbearing potential and has not had a vasectomy must agree to use a barrier method of birth control eg, either condom with spermicidal foam/gel/film/cream/suppository or partner with occlusive cap (diaphragm or cervical/vault caps) with spermicidal foam/gel/film/cream/suppository, and all men must also not donate sperm during the study and for 3 months after receiving the final dose of study drug.
9. Criterion removed per Amendment 1
10. Criterion removed per Amendment 1
11. Criterion removed per Amendment 1
12. A woman of childbearing potential must have a negative serum/urine pregnancy test (highly sensitive serum [β -human chorionic gonadotropin]) within 14 days prior to the first study agent administration.
13. Subject must be willing and able to adhere to the prohibitions and restrictions specified in this protocol, as referenced in the ICF
14. Each subject must sign an ICF indicating that he or she understands the purpose of and procedures required for the study and is willing to participate in the study.

Note: Each subject must sign a separate informed consent form if he or she agrees to provide optional samples for research. If subject agreed to provide optional samples for research study, subject should follow the sample collection schedule that is listed in the optional consent form. Refusal to give consent for the optional research samples does not exclude a subject from participation in the study.

4.2. Exclusion Criteria

Subjects who meet any of the following criteria will be excluded from participating in the study:

1. Criterion modified per Amendment 1:
 - 1.1 No fresh or archived FFPE tumor samples for retrospective biomarker determination
2. Received daratumumab or other anti-CD38 therapies previously
3. Chemotherapy or radiotherapy within 3 weeks before the first study agent administration, or corticosteroids as part of disease treatment within 2 weeks before the first study agent administration, with the exception of an emergency use of corticosteroids such as in the management of severe lymphoma symptoms or life-threatening allergic reaction.
4. Previous allogenic stem cell transplant; or autologous stem cell transplant within

- 12 weeks before the first administration of the study drug
5. History of active malignancy (other than NKTCL) within 2 years before the first study drug administration (exceptions are adequately treated squamous and basal cell carcinomas of the skin, carcinoma in situ of the cervix or breast, or other non-invasive lesion that in the opinion of the investigator, with concurrence with the sponsor's study responsible physician, is considered cured with minimal risk of recurrence within 2 years)
 6. Clinical symptoms of central nervous system (CNS) involvement
 7. Subject has either of the following:
 - a. Known chronic obstructive pulmonary disease (COPD) with a Forced Expiratory Volume in 1 second (FEV1) <50% of predicted normal. Note that FEV1 testing is required for patients suspected of having COPD and subjects must be excluded if FEV1 <50% of predicted
 - b. Known moderate or severe persistent asthma within the past 2 years (refer [Attachment 4](#): National Heart, Lung, and Blood Institute (NHLBI) table of asthma severity), or uncontrolled asthma of any classification. (**Note**: subjects who currently have controlled intermittent asthma or controlled mild persistent asthma are allowed to participate in the study)
 8. Criterion modified per Amendment 4:
 - 8.1 Seropositive for hepatitis B or hepatitis C.

Note: Seropositive for hepatitis B (defined by a positive test for hepatitis B surface antigen [HBsAg]). Subjects with resolved infection (ie, subjects who are HBsAg negative but positive for antibodies to hepatitis B core antigen [Anti-HBc] and/or antibodies to hepatitis B surface antigen [Anti-HBs]) must be screened using real-time polymerase chain reaction (PCR) measurement of hepatitis B virus (HBV) DNA levels. Those who are PCR positive will be excluded. EXCEPTION: Subjects with serologic findings suggestive of HBV vaccination (Anti-HBs positivity as the only serologic marker) AND a known history of prior HBV vaccination, do not need to be tested for HBV DNA by PCR.

If Hepatitis C antibody is positive, RNA PCR needs to be performed and confirmed negative prior to the first study agent administration.
 9. Seropositive for human immunodeficiency virus (HIV)
 10. Unresolved or unstable, serious toxicity from prior administration of another investigational drug and/or of prior cancer treatment.
 11. Subject has any concurrent medical condition or psychiatric condition or disease (eg, active infection, diabetes mellitus, acute diffuse infiltrative pulmonary disease) that is likely to interfere with study procedures or results, or that in the opinion of the investigator would constitute a hazard for participating in this study.
 12. Criterion modified per Amendment 1:
 - 12.1 Subject has clinically significant cardiac disease, including:
 - a. Myocardial infarction within 6 months before the first study agent administration, or unstable or uncontrolled disease/condition related to or

- affecting cardiac function (eg, unstable angina, congestive heart failure, New York Heart Association Class III-IV)
- b. Uncontrolled cardiac arrhythmia (Common Terminology Criteria for Adverse Events [CTCAE] [most recent version] Grade 3 or higher) or clinically significant ECG abnormalities
 - c. Screening 12-lead ECG showing a baseline QT interval as corrected (QTc) >470 msec.
13. Known allergies, hypersensitivity, corticosteroids, monoclonal antibodies or human proteins, or their excipients (refer to respective package inserts or IB), or known sensitivity to mammalian-derived products¹⁸
 14. Known or suspected of not being able to comply with the study protocol (eg, because of alcoholism, drug dependency, or psychological disorder) or the subject has any condition for which, in the opinion of the investigator, participation would not be in the best interest of the subject (eg, compromise their well-being) or that could prevent, limit, or confound the protocol-specified assessments
 15. Invasive investigational medical device within 4 weeks before the screening period or is currently enrolled in an interventional investigational study
 16. Vaccination with live attenuated vaccines within 4 weeks of first study agent administration.
 17. Pregnant or lactating

NOTE: Investigators should ensure that all study enrollment criteria have been met at screening. If a subject's clinical status changes (including any available laboratory results or receipt of additional medical records) after screening but before the first dose of study drug is given such that he or she no longer meets all eligibility criteria, then the subject should be excluded from participation in the study. Section 8.1.2, Screening Phase, describes options for retesting. Section 16.4, Source Documentation, describes the required documentation to support meeting the enrollment criteria.

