- g. Vital signs (blood pressure, temperature, pulse) measured in sitting position. On Cycle 1 Day 1: before the start of daratumumab infusion; at 0.5, 1, 1.5, 2, 3.5 hrs after the start of the infusion; at end of infusion; and 0.5, 1 hr after end of infusion. If an IRR occurred during the infusion due to which infusion is stopped and later the infusion is resumed, the site will follow initial infusion start time point for the vital sign collection. For all other infusions, vital signs will be measured immediately before infusion start and at end of daratumumab infusion.
- h. Refer to SIPP for recommendations on daratumumab infusion rate. Administer pre- and postinfusion medications as per Section 5.3.
- i. May be performed with oral contrast only if the subject is intolerant of IV contrast agents. If other areas of disease are involved, they can be imaged by either CT or MRI. All scans will be collected and reviewed centrally. The similar methodology should be used throughout the study.
- j. Refer to the laboratory manual for the detailed instructions for the whole blood collection.
- k. Follow-up will begin once a subject discontinues study treatment; if subject discontinues due to PD, follow-up will occur at least every 8 weeks (± 2 weeks). If subject discontinues due to other reasons (not PD), follow-up will occur at least every 8 weeks (± 2 weeks), including regular scheduled scan until PD is confirmed, and follow-up visit will be continued after PD confirmation.
- l. If more than one IRRs occurs during dose administration, blood sample should be collected only when the first IRR occurs.
- m. Tumor biopsy may be conducted as clinically indicated and is strongly recommended if lesion is reasonably accessible to confirm suspected PD.
- n. If PET/CT or CT or MRI is performed before ICF signed date due to site's routine practice and if it fulfills the study requirement in the image manual, those image data will be considered as baseline image data as long as the image scanned date is within 21 days prior to Cycle 1 Day 1.
- o. B-Symptoms assessment is also required to be collected in every disease evaluation assessment date.
- p. Local testing for HBsAg, Anti-HBs, and Anti-HBc. Refer to Section 8.6.
- q. For subjects with serologic evidence of resolved HBV infection (ie, positive Anti-HBs or positive Anti-HBc) at Screening, HBV DNA testing by PCR must be performed locally. Refer to Section 8.6.

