7.3. Prohibited Therapies

Use of the treatments listed below is prohibited during the study:

- Prophylactic use of hematopoietic growth factors during Cycle 1
- Other agents that target CD38
- Concurrent radiation therapy is prohibited while on study.
- Administration of commercially available agents with activity against or under investigation for NKTCL, including systemic corticosteroids (≥ 20 mg/day of prednisone or its equivalent per day for more than 7 days during study, unless reviewed/approved by the study responsible physician) (other than those given for IRRs as described in Section 5.3.2) is prohibited.

The sponsor must be notified in advance (or as soon as possible thereafter) of any instances in which prohibited therapies are administered.

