8.2. Efficacy Evaluations

Disease evaluations will be performed at Screening, every 8 weeks (± 7 days) for the first 6 months and thereafter, every 16 weeks (± 7 days) until PD, withdrawal of consent from study participation, or the end of study.

Radiological and PET-CT scans should be performed and collected according to instructions from the independent imaging laboratory. A BICR will be performed to review all the imaging data and clinical information per pre-defined independent central review charter.

The central reviewers will assess disease status based on the Revised Criteria for Response Assessment: LUGANO classification, provided in [Attachment 6](#).¹² Similar methodology should be used for disease assessment at screening and throughout the course of the study. The treatment discontinuation due to PD should be based upon the real time reading results conducted by the central readers. On the basis of clinical information, if PD is confirmed, then for all such subjects, as soon as PD is confirmed by local assessment, the sponsor should be informed immediately.

In order to maximally reduce potential bias between different readers, rigorous methodology will be employed and thus, ensure robustness of the primary endpoint assessment of ORR which is based on BICR. All radiological scans and collected clinical information will be sent to a sponsor appointed Clinical Research Organization (CRO) for a real time BICR. All treatment decisions will be based on such timely central review result. Subjects who are determined to have progressed according to LUGANO classification by the investigator will have scans centrally reviewed for confirmation of objective disease progression. If PD is not confirmed after central review, daratumumab treatment should be continued until centrally documented PD. This procedure may not be followed if the clinical information of subject (eg, Pathologically demonstrated PD) is sufficient enough to demonstrate PD, for such cases, PD confirmation from sponsor study physician is also required.

Definition of Measurable Disease, Assessable Disease, Target Lesion, and Non-Target Lesion

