Attachment 6: Revised Response Criteria for Response Assessment¹²

Response and Site	PET-CT–Based Response	CT-Based Response
Complete	Complete metabolic response	Complete radiologic response (all of the following)
Lymph nodes and extralymphatic sites	Score 1, 2, or 3* with or without a residual mass on 5PS† It is recognized that in Waldeyer’s ring or extranodal sites with high physiologic uptake or with activation within spleen or marrow (eg, with chemotherapy or myeloid colony-stimulating factors), uptake may be greater than normal mediastinum and/or liver. In this circumstance, complete metabolic response may be inferred if uptake at sites of initial involvement is no greater than surrounding normal tissue even if the tissue has high physiologic uptake	Target nodes/nodal masses must regress to ≤ 1.5 cm in LDi; No extralymphatic sites of disease
Nonmeasured lesions	Not applicable	Absent
Organ enlargement	Not applicable	Regress to normal
New lesions	None	None
Bone marrow	No evidence of FDG-avid disease in marrow	Normal by morphology; if indeterminate, IHC negative
Partial	Partial metabolic response	Partial remission (all of the following)
Lymph nodes and extralymphatic sites	Score 4 or 5† with reduced uptake compared with baseline and residual mass(es) of any size	$\geq 50\%$ decrease in SPD of up to 6 target measurable nodes and extranodal sites from baseline; When a lesion is too small to measure on CT, assign 5mm×5mm as the default value; When no longer visible, 0×0mm; For a node > 5mm× 5mm, but smaller than normal, use actual measurement for calculation
Nonmeasured lesions	Not applicable	Absent/normal, regressed, but no increase
Organ enlargement	Not applicable	Spleen must have regressed by >50% in length beyond normal
New lesions	None	None
Bone marrow	Residual uptake higher than uptake in normal marrow but reduced compared with baseline (diffuse uptake compatible with reactive changes from chemotherapy allowed). If there are persistent focal changes in the marrow in the context of a nodal response, consideration should be given to further evaluation with MRI or biopsy or an interval scan	Not applicable
No response or stable disease	No metabolic response	Stable disease
Target nodes/nodal masses, extranodal lesions	Score 4 or 5 with no significant change in FDG uptake from baseline	<50% decrease from baseline in SPD of up to 6 dominant, measurable nodes and extranodal sites; no criteria for progressive disease are met

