2.6. Baseline Measurement

Baseline measurement is defined as the closest non-missing measurement taken on or prior to the date of first study agent administration (including time if available). If the first study treatment date is missing, the corresponding visit date should be used.

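### The response baseline scan can predate permitted lymphoma-directed corticosteroids, and no planned analysis shows whether the single-arm ORR depends on the subjects concerned

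*Protocol*

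**What the plan says.** **Steroids before first dose.** Protocol Section 4.2, criterion 3, excludes "corticosteroids as part of disease treatment within 2 weeks before the first study agent administration, with the exception of an emergency use of corticosteroids". One of its two examples of an emergency is the relief of severe symptoms from the lymphoma itself. The criterion puts no dose, duration or timing limit on the emergency exception. For chemotherapy and radiotherapy it sets 3 weeks.

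**Baseline scan.** Footnote n of the Time and Events Schedule accepts a scan made before consent, provided that it meets the image manual, "as long as the image scanned date is within 21 days prior to Cycle 1 Day 1". Section 8.2 has one pre-dose evaluation: "Disease evaluations will be performed at Screening, every 8 weeks" thereafter for the first 6 months. SAP Section 2.6 takes as baseline the "closest non-missing measurement taken on or prior to the date of first study agent administration".

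**Response.** In Attachment 6, a PET-CT partial response is a score of 4 or 5 "with reduced uptake compared with baseline and residual mass(es) of any size".

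**Analysis.** The primary ORR counts every BICR-assessed CR or PR among all treated subjects (SAP Sections 2.8.1, 5.1 and 5.2.1). The one sensitivity analysis substitutes the investigator's assessment (SAP Section 5.1).

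**The concern.** Baseline should describe the tumour as it stands when daratumumab starts. For chemotherapy and radiotherapy the 3-week washout matches the 21-day scan window, so neither can fall between scan and first dose. Steroids can, by two routes:

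- Non-emergency lymphoma-directed steroids after a scan near Day -21, stopped by about Day -15.
- Emergency steroids for severe lymphoma symptoms at any time between the scan and the first dose.

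The protocol itself treats steroids as relevant to the disease. Section 7.3 restricts "Administration of commercially available agents with activity against or under investigation for NKTCL, including systemic corticosteroids" above a stated dose and duration, and criterion 3 gives them a washout.

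A steroid effect followed by disease control could be scored as PR against the older scan. For a subject who would otherwise not respond, this error can only raise the ORR, and a single-arm trial has no control group to offset it. At stake is the test of the 15% null, where 8 responders among 32 are enough to reject. The investigator-assessment sensitivity analysis would normally share the same baseline scan and so would not reveal the problem.

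**Working it through.** **1. Order of events allowed by the text**

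| Item | Earliest | Latest | Source |
|---|---|---|---|
| Baseline scan | Day -21 | before first dose | Time and Events Schedule, footnote n |
| Non-emergency lymphoma-directed steroids | no limit | about Day -15 | Section 4.2, criterion 3 |
| Emergency steroids | no limit | up to first dose | Section 4.2, criterion 3 |
| First response scan | Week 8, ±7 days | | Section 8.2 |

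Nothing in the protocol or SAP places the scan after the steroids. The SAP's closest-measurement rule helps only if a second pre-dose scan happens to exist.

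**2. The plan's own design figures**

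Inputs (Protocol Sections 10.2 and 10.9; SAP Sections 1.4 and 3): p0 = 0.15, p1 = 0.30, continue if at least 2 of 15 respond, reject if at least 8 of 32 respond.

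P(reject | p) = Σ over x = 2 to 15 of P[Bin(15, p) = x] × P[Bin(17, p) ≥ 8 − x]

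- p = 0.15: 0.094, against the stated 10% ceiling.
- p = 0.30: 0.781, against the stated 78%.
- With futility ignored, as a non-binding rule allows: 0.096 and 0.788.

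The design reproduces.

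**3. Effect of exposure, under assumptions**

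Let u be the share of subjects given lymphoma-directed steroids between scan and first dose, and q the chance that an exposed subject who would not respond to daratumumab is nevertheless scored CR or PR. The documents give neither. At a true ORR of 15% the apparent rate is

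p = 0.15 + 0.85 × u × q

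| u | q | apparent ORR | P(reject) |
|---|---|---|---|
| 0 | – | 15.0% | 9.4% |
| 3% | 10% | 15.3% | 10.1% |
| 5% | 10% | 15.4% | 10.6% |
| 5% | 25% | 16.1% | 12.7% |
| 10% | 10% | 15.9% | 12.0% |
| 10% | 25% | 17.1% | 16.6% |

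For example, 0.15 + 0.85 × 0.10 × 0.25 = 0.171. Of 32 subjects, u = 3% is about 1 exposed subject (32 × 0.03 = 0.96), and u = 10% is about 3 (32 × 0.10 = 3.2).

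**4. Exactly one subject wrongly credited**

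Fix one subject as a responder and let the other 31 respond at 15%. P(reject) is 0.167 if that subject is in stage 2 and 0.172 if in stage 1, so about 17%. The observed ORR gains up to 1/32 = 3.1 percentage points. This is conditional on a wrong credit having occurred; it does not say how likely one is.

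**5. Protocol steroids received by everyone before Week 8**

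If all 8 weekly infusions are given, methylprednisolone before infusion totals 2 × 100 + 6 × 60 = 560 mg (Section 5.3.1), and after infusions 1 to 3 it totals 3 × 2 × 20 = 120 mg (Section 5.3.2). The sum is 680 mg.

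**The case against.** The case for leaving the plan alone has real force.

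- **Background steroids.** With about 680 mg of protocol steroid in every subject by Week 8, the ORR already describes daratumumab plus its premedication. Re-ordering one scan does not isolate the antibody. This stands and limits the size of the concern. It does not remove it, because premedication is part of the tested regimen and falls after baseline and with treatment in everyone; a pre-dose course does neither.
- **Persistence.** The first response scan comes at Week 8, about 10 weeks after a non-emergency course must have stopped. A transient effect in fast-moving disease may well be gone. This stands.
- **Response criteria.** A reader might infer that any drop in uptake, however slight, is a PR. Attachment 6 does not support that: a score of 4 or 5 without significant change in uptake is no metabolic response, and PR also requires no new lesions.
- **Limits on steroids.** A reader might infer that pre-dose steroids are unlimited. The exception is confined to emergencies. Section 7.3 restricts prednisone-equivalent doses of 20 mg/day or more for over 7 days during the study unless approved; since Section 3.1 counts screening as participation, that arguably applies from consent. Shorter courses, and any before consent, remain possible.
- **Unseen documents.** The image manual and BICR charter were not available and might contain a rule.
- **Rescanning.** A baseline taken just after emergency steroids may show suppressed disease, so that rebound hides a response or reads as progression, and the repeat is an extra procedure in a very ill patient. This stands and rules out a mandatory repeat scan.

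**Conclusion.** The gap is real and its likely effect is modest. The protocol allows some subjects to be assessed against a pre-steroid baseline, and neither document identifies those subjects or tests whether the result depends on them.

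Under assumed exposure of 3% to 10% and mis-scoring of 10% to 25%, the rejection probability at a true ORR of 15% runs from 10.1% to 16.6%, against 9.4% as designed. At the low end it is practically the planned 10%. The 17% figure assumes that one wrong credit has already happened.

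A reader might go further and conclude that steroid shrinkage is in fact credited to daratumumab in the primary ORR, or that the error rate is several times the planned one. The documents do not support either: they give no count of exposed subjects, no size or duration of steroid effect, and no reason to expect more than a few such cases. Larger figures follow only from assuming that two or more subjects are wrongly scored. What the documents do support is an inexpensive safeguard for a single-arm primary endpoint.

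**What to change.** 1. **SAP Section 5.2.2.** Prespecify a supportive ORR with exact 95% CI in which any subject who had lymphoma-directed corticosteroids between the baseline scan and the first dose counts as a non-responder. List those subjects.
2. **Data collection (Protocol Section 7, eCRF).** Collect full start and stop dates for such steroids from the date of the baseline scan, including before consent. At present concomitant medication is recorded from consent, and earlier records cover prior oncologic therapy. SAP Section 2.7.3 imputes a missing day for concomitant medication as the 15th, which is too coarse to order a scan and a steroid course within 21 days.
3. **Protocol footnote n and Section 8.2.** State that where non-emergency disease-directed steroids are given, the baseline scan used for response is scheduled after the last such dose, within the existing 21-day window.

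Do not require a repeat scan after emergency steroids; the supportive analysis covers those subjects. Steroid use, washout length, dosing and sample size stay as they are.

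Cost: slightly later scan scheduling for a few subjects, a small addition to data collection, and one extra analysis. The supportive ORR is conservative, because it also discards genuine daratumumab responses in exposed subjects, so it should be read beside the primary ORR and not replace it.
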